3.1 Study Data Collection

Standardized Case Report Forms (CRFs) will be provided to all participating sites. Data will be reviewed by the study monitor and data management to identify inconsistent or missing data and to ensure compliance with the study protocol.

3.2 Confidentiality

All information and data concerning study subjects will be considered confidential, and handled in compliance with all applicable regulations including the requirements of the Health Insurance Portability and Accountability Act (HIPAA) of 1996.

ZELTIQ P/N: [REDACTED]
Protocol Number: ZA18-003

Only authorized site staff, the study Sponsor or the Sponsor's designee, IRB and FDA will have access to these confidential files. All data used in the analysis, reporting and publication of this clinical trial will be maintained without identifiable reference to the subject. Any data that may be published in abstracts, scientific journals, or presented at medical meetings will reference a unique subject code and will not reveal the subject's identity.

3.3 *Investigator Responsibilities*

General Responsibilities

Investigators are responsible for ensuring the investigation is conducted according to all signed agreements, the Investigational Plan, and applicable FDA regulations.

The Investigator must protect the rights, safety, privacy and welfare of the subjects under the Investigator's care. Investigators will assume overall responsibility and accountability for study site staff and for the clinical data obtained during the study.

The Investigator assumes all responsibilities per 21 CFR 812 and other applicable regulations, including but not limited to:

IRB approval: The Investigator may not begin the study until the governing institutional review board (IRB) provide written approval of the study protocol and consent form. The Investigator is also responsible for fulfilling any conditions of approval imposed by the IRB.

Informed Consent: The Investigator must ensure that informed consent is obtained from each prospective study subject in accordance with 21 CFR Part 50 and that the study is not commenced until IRB approvals have been obtained.

Device Accountability: The Investigator is responsible for controlling all investigational device(s) stored at their site, including supervision of device use, disposal of the device or returning the device as instructed by the Sponsor. (21 CFR 812.110 & 812.140 (2))

Financial Disclosure: Investigators shall provide financial disclosure according to federal regulations (21 CFR 54).

Study Coordinator: To assure proper execution of the study protocol, each Investigator must identify a study coordinator for the site who will work with and under the authority of the Investigator to assure that study requirements are fulfilled as appropriate.

Investigator Records

The Investigator and study staff must maintain accurate, complete, and current records relating to the conduct of the investigation. Records must be retained for a period of two years following (1) the date the investigation was completed or terminated, or (2) the records are no longer required to support a regulatory submission or completion of a product development protocol, whichever is longer. Participating Investigators shall maintain the following:

- All correspondence with the Sponsor, another Investigator, the IRB, or a monitor
- Records of all persons authorized to conduct the study (e.g. Delegation of Duties/Signature Authorization, CV)
- Records of receipt, use or disposition of the devices
- Informed Consent documentation for all enrolled subjects
- Records of each subject's case history, including study-required Case Report Forms and source documentation (e.g. physician notes, lab reports, study worksheets, clinic charts)
- All relevant observations of adverse device effects
- Records of any protocol deviations
- The condition of each subject upon entering and during the course of the investigation and any relevant medical history and results of any diagnostic tests
- Record of each subject's exposure to the devices, including the date and time of use
- Investigational plan with all amendments
- Current IRB approved informed consent and all previously approved versions
- Signed Investigator agreement
- Investigators will be responsible for the accurate and timely completion of CRFs during the trial.

These records must be available and suitable for inspection at any time by Sponsor representatives (monitor) or the reviewing IRB. The Investigator will supply access to study-related medical records, original laboratory data, and other records and data as they relate to the trial. The Investigator will ensure that both he/she and his/her

ZELTIQ P/N: [REDACTED]
Protocol Number: ZA18-003

study staff have adequate time and resources to devote to the study, including study enrollment, subject evaluations, study documentation and site monitoring.

Investigator Reports

The Investigator is responsible for preparation and submission of the following reports:

- Report of any unanticipated adverse device effects shall be submitted to the Sponsor within 24 hours and no later than 10 working days after the Investigator first learns of the effect.
- Withdrawal of IRB approval of the Investigator's part in the investigation shall be reported to the Sponsor within 5 working days
- Progress reports on the investigation to the Sponsor, the monitor, and the reviewing IRB annually. Alternatively, the Sponsor may prepare the report.
- Deviations from the investigational plan shall be reported to the Sponsor and the IRB.
- Failure to obtain informed consent prior to use of a device in a subject shall be reported to the Sponsor and IRB within 5 working days after the use occurs.
- A final report shall be submitted to the Sponsor and IRB within 3 months after termination or completion of the investigation, or the Investigator's part of the investigation.

3.4 Sponsor Responsibilities

General Responsibilities:

As the Sponsor, ZELTIQ Aesthetics assumes overall responsibility for the conduct of the study. ZELTIQ Aesthetics assumes all responsibilities per 21 CFR 812 and other applicable regulations, and shall:

IRB approval: Ensure IRB approval for the investigation before shipping the device to any Investigator.

Investigators: Select Investigators qualified by training and experience, and providing them with the information they need to conduct the investigation properly (21 CFR 812.43). Obtain a signed Investigator Agreement (21 CFR 812.43(c)) from each participating Investigator. Study sites will be evaluated to ensure that they have an adequate patient base and can provide sufficient staff and documentation support to conduct the study properly.

ZELTIQ P/N: [REDACTED]
Protocol Number: ZA18-003

Monitoring: Select monitors qualified by training and experience to monitoring the study (21 CFR 812.43), and ensure proper monitoring of the investigation. (21 CFR 812.46)

Investigational devices: Provide devices only to qualified Investigators (21 CFR 812.43). No study site may receive shipment of study devices until the following documents are received by the Sponsor:

- Signed Investigator's Letter of Agreement
- Signed Clinical Site Agreement
- Investigator current curriculum vitae

Data Management and analysis: Ensure data collection, verification, analysis, records storage, etc. Sponsor will assist with presentation(s) and/or publication(s).

Training

Study Training: To ensure uniform data collection and protocol compliance, Sponsor personnel will provide an educational session to study site personnel as needed, which will cover the Investigational Plan, techniques for the identification of eligible subjects, data collection and form completion, and the device directions for use. The Investigator and study staff will be trained on the study devices and protocol, applicable regulations and requirements, and expectations of the study, enrollment expectations, subject selection, informed consent, required clinical data and record keeping, etc.

Investigational Device Use: Representatives of the Sponsor will train Investigators in use of the study device prior to study initiation. Sponsor representatives may be present at study procedures.

Site Monitoring

The Sponsor will ensure that qualified clinical monitors are available to monitor and oversee the conduct of the trial and that monitoring is performed in accordance with the Sponsor's approved procedures or third-party procedures approved by the Sponsor.

The clinical monitors will evaluate compliance with the investigational plan, FDA regulations, any specific recommendations made by the site's IRB and the signed Investigator Agreement.

Monitoring Visits

ZELTIQ P/N: [REDACTED]

Protocol Number: ZA18-003

On-site monitoring visits will assess the progress of the clinical study and identify any concerns that result from device performance or review of the Investigator's study records, study management documents, and informed consent documents.

Monitoring will ensure continued protocol compliance, accurate data reporting, and adequate accounting of shipments of study devices. Monitoring visits will occur at minimum once before study close-out.

During monitoring visits, the monitor will compare subject records and other supporting documents with reports at the site to determine that;

- The facilities used by the investigation continue to be acceptable for the purposes of the clinical study
- Informed consent was properly obtained and documented for all enrolled study participants
- The Investigational Plan is being followed, and only eligible subjects are being enrolled into the study
- Deviations to the Investigational Plan have been reported to ZELTIQ and the IRB, as appropriate
- Adverse events are promptly being reported
- Device accountability is being maintained
- Information recorded in the case report forms and study reports are accurate, complete, legible and consistent with source documentation.
- Subjects failing to complete the clinical study and the reason for failure are recorded.
- Missed follow-up visits are noted in the study documentation

Clinical monitors will provide feedback to the site regarding protocol or study compliance.

Study Site Closeout

At the close of the study at an investigational site, the monitor will ensure that all case report forms have been monitored and retrieved and that the Investigator's files are accurate and complete. The monitor will ensure that all investigational devices and study supplies are accounted for, and provide for appropriate disposition of any remaining supplies. The monitor will review record retention requirements with the

ZELTIQ P/N: [REDACTED]
Protocol Number: ZA18-003

Investigator and any remaining Investigator obligations are reviewed and ensure that all applicable requirements are met for the study. The monitor will prepare a report of the site closeout visit.

Final Report

A final report will be prepared at the conclusion of the trial. Copies of the final report will be provided to each Investigator and to the respective IRB.

4. Data Ownership

ZELTIQ Aesthetics, the study Sponsor, retains ownership of all data generated in this study, and controls the use of the data for purposes of regulatory submissions to the US and/or other governments. Investigator(s) and institution(s) (which shall include their employees, agents, and representatives) may not issue or disseminate any press release or statement, nor initiate any communication of information regarding this study (written or oral) to the communications media or third parties without the prior written consent of the Sponsor.

5. Publication Policy

Participating Investigators and/or Institutions may publish information or data collected or produced as a result of participation in appropriate scientific conference or journals or other professional publications subject to written permission from the Sponsor, provided that drafts of the material are provided to the Sponsor for purposes of review and comment at least sixty (60) days prior to the first submission for publication or public release. Investigators may not publish information regarding site-specific data until a multicenter study report has been published.

6. Risk/Benefit Analysis

The Sponsor has undertaken a comprehensive risk-benefit analysis.

6.1 Benefits

Abdominal muscle toning and contouring in the treatment area is anticipated to provide an aesthetic benefit and this non-invasive device accomplishes the desired effect without anesthesia and with minimal recovery time. Furthermore, the results of this study will help in the development of the optimal aesthetic procedure for fat removal with cryolipolysis followed by EMS. Considering the number of body contouring surgical procedures performed for the removal of fat each year (1.3 million procedures worldwide, according to the 2011 International Society of Aesthetic Plastic Surgeons Biennial Global Survey), the use of such a non-invasive

ZELTIQ P/N: [REDACTED]
Protocol Number: ZA18-003

procedure has the potential to significantly reduce the incidence of complications and post-surgical limitations associated with those procedures.

6.2 Risks

Although this study presents minimal risks to the subject, there is always the potential for some risk when a medical procedure is performed.

Anticipated Device Effects from CoolSculpting procedure:

These are known effects of the ZELTIQ Procedure, previously noted in prior studies as transient and/or temporary effects related to the treatment. Anticipated effects of the device which will not be considered adverse events include:

- inflammation of the subcutaneous fat layer, which is a desired effect of the procedure;
- sensations of coldness, stinging, burning, pinching, or pressure associated with placement of the applicator and the initiation of the cold treatment;
- known skin effects (e.g., blanching; erythema, bruising, purpura, petechiae, swelling, discomfort, tenderness, or soreness at the treatment site, all mild to moderate in nature) which are temporary effects that resolve spontaneously shortly after the procedure;
- transient, localized sensory changes (e.g., numbness, tingling) resolving within 12 weeks of the procedure;

Anticipated Device Effects of EMS:

- muscular pain in the treatment area
- temporary muscle spasm
- temporary joint or tendon pain
- local erythema and/or skin redness
- skin irritation and burns under the electrodes may cause possible allergic skin reaction to tape or gel

Adverse Effects

The following summarizes the potential adverse effects in this study:

Potential Adverse Effect	Description
Severe Bruising	The appearance of bruising (purple discoloration); purpura (purple colored spots or patches); or petechiae (pin point red dots) that is rated as severe by the Investigator;
Prolonged Bruising	Bruising lasting longer than 1 month
Severe Erythema	The appearance of erythema (redness) that is rated as severe by the Investigator
Prolonged Erythema	Erythema lasting longer than 2 weeks.
Severe Swelling	The appearance of swelling (edema) that is rated as severe by the Investigator
Prolonged Swelling	Swelling lasting longer than 1 month.
First Degree Burn	A first degree burn is superficial and causes local inflammation of the skin. The inflammation is characterized by pain, redness, and mild swelling. The skin may be very tender to touch.
Second Degree Burn	Second degree burns are deeper and in addition to the pain, redness and inflammation, there is also blistering of the skin.
Third Degree Burn	Third degree burns are deeper still, involving all layers of the skin. Because the nerves and blood vessels are damaged, third degree burns appear white, leathery and tend to be relatively painless.
Cold-Induced Panniculitis	Severe inflammation which requires medical or surgical intervention.
Skin Pigmentary Changes	The appearance of hyperpigmentation or hypopigmentation in the treatment area.
Infection	Infection at the treatment site, diagnosed by a Physician and requiring medical intervention.
Discomfort During Procedure	Discomfort during the procedure that is intolerable to the subject and results in an interruption or discontinuation of the procedure.
Discomfort Post Procedure	Significant discomfort, pain, cramping, tenderness, soreness, muscle spasm following the procedure which results in medical intervention (physician visit and/or prescription pain reliever)
Prolonged Sensory Alteration Post Procedure	Sensory changes (numbness, tingling, burning sensation) that are prolonged (i.e., lasting longer than 12 weeks).
Sensory Alteration Requiring Medical Intervention	Sensory changes (pain, burning, stinging, hypersensitivity) with a severity warranting medical intervention.
Vasovagal Symptoms	The occurrence of symptoms of anxiety, lightheadedness, dizziness, nausea, sweating, near syncope, or syncope (fainting).

ZELTIQ P/N: [REDACTED]
Protocol Number: ZA18-003

Potential Adverse Effect	Description
Gastrointestinal Symptoms	Nausea, bloating, or diarrhea temporally related to the procedure (within the first few hours after the procedure)
Contour Irregularity	Significant indentation or contour irregularity in the treatment area that would require surgical intervention.
Skin surface irregularities	Significant indentation or rippling which develops 1 month after treatment that would require medical intervention.
Allergic/Irritant Contact Dermatitis	Itchy rashes and skin peeling that may result from prolonged exposure to gel or gelpad, foam borders or applicator pressure
Subcutaneous Induration	Hardness within the treatment area, either as generalized firmness or discrete nodules.
Hernia	Creation or exacerbation of hernia. Hernia is defined as a protrusion of an organ or the fascia of an organ through the wall of the cavity that normally contains it.
Paradoxical Hyperplasia	Visibly enlarged tissue volume within the treatment area which may develop 2-5 months after treatment. Surgical intervention may be required.

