2.2 Study Duration

Enrollment and follow-up is expected to take up to six (6) months for each subject.

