2.13 Follow-up Procedures

Subjects who receive study treatment with the study devices will be required to complete all follow-up visits and assessments (2-Week, 4-Week and 12-Week).

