2.13.3 Twelve-week Post Final Treatment Follow-Up Visit; 12 Weeks ± 2 weeks

The following evaluations will be performed at the 12-week post final treatment follow-up visit:

- i. Obtain weight.
- ii. Clinical assessment of the treatment area for any epidermal, dermal, and subcutaneous findings (e.g., erythema, bruising, swelling, pigment changes) as well as alterations in sensation (e.g., numbness, tingling).
- iii. Assessment of any adverse events.
- iv. Obtain 3-Dimensional photographs of the abdomen using Vectra or similar imaging system.
- v. Obtain photographs of the treatment area using standardized setup and settings. See Section 2.14 for details.
- vi. Subject to complete Global Aesthetic Improvement Scale.

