2.13.4 Optional Follow-Up Evaluations (up to 4 within study period)

The full evaluation is not required at optional follow-up visits; the extent of the assessment will be at the discretion of the Investigator.

Table 3 summarizes the study schedule and events at each visit.

Table 3. Schedule of Visits

	Screening (< 1hr)	Photo Visit (<1hr)	EMS Treatment #1 (<2hrs)	EMS Treatment #2 (<2hrs)	EMS Treatment #3 (<2hrs)	EMS Treatment #4 (<2hrs)	CoolSculpting Treatment (<4hrs)	2-Wk Post Tx Phone Follow-Up (<30 min)	4-Wk Post-Tx Follow-Up 12-Wk Post- Tx Follow-Up<br (<="" 1="" hr)<="" th=""/>Optional Follow- Up*****		12-Wk Post- Tx Follow-Up Optional Follow- Up*****	Optional Follow- Up*****
Time Frame	Day -60 to 0	Day -30 to 1	Day 0	Week 1	Week 2	Week 2	Day 0- Day 10 ±3 days	Week 2-3****	(4 ± 1 weeks)	(12 ± 2 weeks)	Open
Informed Consent***	X										
Eligibility Criteria	X		X	X	X	X	X				
Medical History	X										
Tx Site Assessment	X		X	X	X	X	X		X	X	
Height	X										
Weight	X	X	X				X		X	X	
BMI	X										
3D Photography		X				X			X	X	
Standardized Photography		X				X [#]			X [#]	X	
CoolSculpting							X ^{**}				
EMS			X*	X*	X*	X*					
Pain Assessment			X	X	X	X	X	X	X	X	
AE Assessment			X	X	X	X		X	X	X	
Subject GAIS										X	

* EMS treatment visits 1, 2, 3, 4 apply to Cohorts 1, 2 and 4 only.

** Cohort 2 after EMS and Cohort 3.

*** Informed Consent to be signed by subject prior to the collection of any data or initiation of any study procedures.

**** 2-week F/U timing is dependent on cohort assignment.

***** Investigator discretion as to timing and extent of follow-up assessment for optional visits.

Optional

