 - o In general, hospitalization signifies that the participant has been detained (usually involving at least an overnight stay) at the hospital or emergency ward for observation and/or treatment that would not have been appropriate in the physician's office or outpatient setting. Complications that occur during hospitalization are AEs. If a complication prolongs hospitalization or fulfills any other serious criteria, the event is serious. When in doubt as to whether hospitalization occurred or was necessary, the AE should be considered serious. Hospitalization for elective treatment of a pre-existing condition that did not worsen from baseline is not considered an AE.
- e. results in medical or surgical intervention to prevent impairment to body structure or function;
- f. results in fetal distress, fetal death, or a congenital abnormality/birth defect.

Time Period and Frequency for Collecting AE and SAE Information

All AEs and SAEs from the signing of the ICF until the follow-up visit will be collected at the time points specified in the schedule of activities, and as observed or reported spontaneously by study participants.

Medical occurrences that begin after signing of informed consent and before administration of study treatment will be recorded on the Medical History/Current Medical Conditions section of the CRF not the AE section.

Unanticipated Adverse Device Effect (UADE)

Any serious adverse effect on health and safety or any life-threatening problem or death caused by, or associated with a device, if that effect, problem, or death was not previously identified in nature, severity, or degree of incidence in the investigational plan or application, or any other unanticipated serious problem associated with a device that relates to the rights, safety, or welfare of participants.

The Investigator shall be responsible for determination of the causal relationship of all adverse events to the device and/or procedure. The Principal Investigator is responsible for monitoring the safety of the participants enrolled.

Reportable Incidents

ZELTIQ P/N: [REDACTED]
Protocol Number: ZA18-003

Serious adverse events (SAEs) and unanticipated adverse device effects (UADEs) must be recorded and reported to the manufacturer of the study device and to the Sponsor or designee within 24 hours of knowledge of the event.

Sponsor Contact:

[name]
Director, Clinical Trial Management
ZELTIQ Aesthetics, an Allergan affiliate
[name]

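### In Cohort 2, and in Cohort 3 subjects who do not go on to Cohort 4, required adverse-event follow-up ends with 59-90% of the protocol's own onset window for paradoxical hyperplasia still to come

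*Combined protocol and SAP*

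**What the plan says.** Section 6.2 lists paradoxical hyperplasia among the potential adverse effects: "Visibly enlarged tissue volume within the treatment area which may develop 2-5 months after treatment". It adds that surgery may be needed.

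Section 2.13 requires follow-up at 2, 4 and 12 weeks only. The last of these is headed "Twelve-week Post Final Treatment Follow-Up Visit; 12 Weeks ± 2 weeks". Section 2.18 sets the collection period: "All AEs and SAEs from the signing of the ICF until the follow-up visit will be collected" at the scheduled time points, together with events that are observed or reported spontaneously. It does not say which follow-up visit is meant. In Table 3 the last column marked for AE assessment is the 12-week visit.

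Section 2.13.4 allows up to four optional evaluations, but "the extent of the assessment will be at the discretion of the Investigator", and Table 3 leaves their timing open and marks no AE assessment for them. Section 2.2 states: "Enrollment and follow-up is expected to take up to six (6) months for each subject". Section 2.16.3 plans a descriptive count and percentage of subjects for every AE term.

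**The concern.** The plan gives an onset period for a listed device effect and then schedules its last AE assessment early in that period for the subjects whose final treatment is CoolSculpting. A case that appears in month 4 or 5 would reach the database only if the subject called the site or the investigator happened to arrange an optional visit.

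The effect matters because it may need surgery and because it is enlargement in a study of contour improvement. The final report will carry a percentage for this term if the term is recorded. If it is not, the silence will be read as zero. Either way, readers may take the figure as covering the whole risk period when it covers a minority of it.

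**Working it through.** The plan gives no rate, onset distribution or coverage figure for this effect, so there is no figure of its own to reproduce. The check compares the two time scales.

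**Inputs**
- Onset window: 2 to 5 months after treatment (section 6.2). At 30.4375 days per month this is 2 × 30.4375 = 60.9 to 5 × 30.4375 = 152.2 days, a width of 91.3 days.
- Last required visit: 12 ± 2 weeks after the final treatment (section 2.13.3), that is 70, 84 or 98 days.
- Final treatment: CoolSculpting in Cohorts 2 and 3 (Table 2, sections 2.12.2 and 2.12.3); EMS in Cohort 4 (section 2.12.4). Cohort 1 receives no CoolSculpting.
- Cohort 4 gap from CoolSculpting: at most 6 months (section 2.7, inclusion criterion g), with no minimum stated.
- EMS course: four sessions within two weeks, the third and fourth in Week 2 (sections 2.12.4 and 2.12.5). I take 8 to 14 days; the 8 is an assumption.

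**Cohort 2, and Cohort 3 without transfer**

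Share of the window after the last required visit at T days = (152.2 − T) / 91.3.

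| T (days) | Calculation | Share without scheduled contact |
|---|---|---|
| 70 | 82.2 / 91.3 | 90% |
| 84 | 68.2 / 91.3 | 75% |
| 98 | 54.2 / 91.3 | 59% |

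The result depends little on how a month is counted. With 30-day months it is (150 − T) / 90, or 58-89%. With 4-week months it is (140 − T) / 84, or 50-83%.

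**Cohort 4**

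Here T = gap + EMS span + days to the final visit, from gap + 8 + 70 to gap + 14 + 98.

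| Assumed gap (days) | T (days) | Share without scheduled contact |
|---|---|---|
| 0 | 78-112 | 44-81% |
| 28 | 106-140 | 13-51% |
| 56 | 134-168 | 0-20% |
| 70 | 148-182 | 0-5% |
| 84 | 162-196 | 0% |

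The smallest gap that gives full cover is 152.2 − span − visit. At nominal timing this is 152.2 − 14 − 84 = 54 days (about 8 weeks). In the least favourable case it is 152.2 − 8 − 70 = 74 days (about 11 weeks).

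**Does a 5-month contact fit the stated duration?**

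Six months is 6 × 30.4375 = 183 days. Section 2.10 defines enrolment as the start of study treatment. Counted from there, Cohort 3 reaches 5 months at Day 152. In Cohort 2, CoolSculpting falls at the latest on Day 14 + 7 = 21 under section 2.12.2 (Table 3 has it earlier), so 5 months is reached at Day 21 + 152 = 173. Both fit. If the full 60-day screening window counted as well, the totals would be 60 + 152 = 212 and 60 + 21 + 152 = 233 days, and neither would fit.

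**The case against.** The strongest reply is that this is a feasibility study whose safety endpoint is unanticipated adverse device effects. Listing a risk is not a promise to estimate its rate, and at most 60 subjects could not estimate it well: with zero events in 60, the exact two-sided 95% upper limit is 1 − 0.025^(1/60) = 6.0% even with complete follow-up. All of that stands, and it limits how much weight the point carries. It does not remove the mismatch, because the plan does commit to a percentage for each AE term.

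A second reply is that AE collection does not literally stop at week 12. Section 2.18 assesses AEs continuously and accepts spontaneous reports, optional visits are open in timing, and each subject has up to six months. This is also fair. These routes may catch late cases, but none requires a contact after week 12, so the point is confined to scheduled ascertainment.

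A reader might infer four stronger things that the documents do not support:
- That the 59-90% applies to the whole study. It does not apply to Cohort 1, and mostly not to Cohort 4.
- That 59-90% of cases will be missed, or that incidence will certainly be understated. A share of a calendar window is not a share of cases, and no onset distribution is given. Only if onset were assumed uniform over the window would the last visit have seen 10-41% of cases.
- That a subject moving from Cohort 3 to Cohort 4 has CoolSculpting events diverted to medical history. The rule concerns "Medical occurrences that begin after signing of informed consent and before administration of study treatment". The documents describe no second consent. Section 2.10 defines treatment initiation by any study device, and section 2.12.4 treats the earlier CoolSculpting as part of this same protocol. On that reading, study treatment has already been given.
- That the primary photographic endpoint is compromised. It is defined at 12 weeks, so later changes lie outside it by definition.

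**Conclusion.** The point holds for Cohort 2 and for Cohort 3 subjects who do not enter Cohort 4. For them, required AE ascertainment covers only 10-41% of the onset window that the protocol itself gives, leaving 59-90% (75% at nominal timing) without scheduled contact. The reported frequency of paradoxical hyperplasia may be understated there; by how much cannot be said from the documents.

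The figure rests on calendar months of 30.4 days and on the 12-week visit taking place within its window. For Cohort 4 the answer depends on the gap between CoolSculpting and EMS, for which no minimum is stated: cover is full at nominal timing from about 8 weeks, and in the least favourable timing from about 11 weeks.

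**What to change.** Reconcile sections 2.2, 2.13, 2.18, Table 3 and the risk table as follows.

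- For Cohort 2, and for Cohort 3 subjects who do not enter Cohort 4, make one of the optional follow-ups a required AE contact by phone or email about 5 months after CoolSculpting, and mark it in Table 3. Section 2.13.1 already uses this type of contact at 2 weeks and already lets the investigator call the subject in if an AE is suspected. That matters here, because a remote contact relies on the subject noticing the change. A Cohort 4 subject whose 12-week visit falls before Day 152 after CoolSculpting could be handled in the same way.
- Name this contact in section 2.18 as the end of AE collection for these subjects, in place of an unnamed follow-up visit.
- State in section 2.2 that the six months run from enrolment as section 2.10 defines it.

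The cost is one short contact for each subject concerned and a later database lock for the last of them, by about 152 − 84 = 68 days, or some 2 months.

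If no later contact is added, report the count and percentage for paradoxical hyperplasia by cohort with the duration of follow-up after CoolSculpting, and state that zero cases does not exclude later onset. This costs only a table column and a sentence.
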